9.12 Minimal Symptom Expression

The Minimal Symptom Expression is defined as MG-ADL score of 0 or 1 (Vissing et al. 2020). The complete list of MG-ADL items and scores are provided in [Table 13-3](#). The total score will be calculated according to the rules set down in [Section 13.3](#).

The number and percentage of participants achieving Minimal Symptom Expression at any time during the Treatment and Observation Periods will be summarized by study cycle, actual dose level received within study cycle, and RLZ total using descriptive statistics.

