8.1.4 Patient-reported outcomes

Patient-reported outcomes must be completed as per time points mentioned in the Schedule of Activities (Section 1.3). The PROs should be completed prior to any intrusive procedures in a quiet place.

The PROs should be completed in the following order: MG-ADL, MG Symptoms PRO, EQ-5D-5L, and MG-QOL15r. The PROs should only be checked for completeness. On dosing days, the

PROs will be completed prior to dosing. Study participants should not take pyridostigmine (or other AChE inhibitor medication) from midnight before the days when efficacy assessments are performed, when medically safe to do so to standardize testing.

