9.2.1 Intercurrent event handling rationale and impact on the study

In MG0007, every study participant, except those coming from MG0004, will start with an initial fixed mandatory cycle. Prior to dosing in the initial fixed treatment cycle, the study participant will be assessed for MG worsening (eg, an increase of 2.0 points on the MG-ADL or 3.0 points on the QMG scale). The study participant will be initially randomized to rozanolixizumab equivalent to approximately 7mg/kg or 10mg/kg weekly (QW). After the first treatment cycle, dose adjustments may be applied at the start of each treatment cycle based on Investigator's discretion. Dose adjustments may not be applied during a treatment cycle.

For the assessment of safety and tolerability, adverse events (AEs) recorded up to 8 weeks after the last sc infusion will be utilized for main analyses, regardless of study participants receiving treatment with rescue therapy.

For the analyses of efficacy endpoints, the intercurrent events to be considered are the use of rescue therapy prior to Day 43 and permanent treatment discontinuation (or withdrawal from study) due to TEAEs. Efficacy endpoints will be summarized in line with a treatment policy approach. With this approach, rozanolixizumab results will be analyzed regardless of study participants receiving treatment with rescue therapy. Summaries will also be presented for the efficacy endpoints where participants will be censored at the time that they take rescue medication.

Missing values will not be imputed.

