9.4 Planned efficacy and other analyses

9.4.1 Efficacy analyses

The main efficacy endpoint is the "Change from Baseline (Day 1) to Day 43 in MG-ADL score," for each of the first three 6-week treatment cycles where the Baseline of the respective cycle will be used as reference.

The summaries will be provided overall and by randomized treatment in-line with a treatment policy approach. Observed results will be presented for the different cycles (1 to n) regardless of the first cycle being mandatory or not. Missing values will not be imputed. Further summaries will be presented by the treatment received in each cycle.

The other secondary efficacy endpoints, Change from Baseline (Day 1) to Day 43 in QMG score, Change from Baseline (Day 1) to Day 43 in MG-C score, Change from Baseline (Day 1) to Day 43 in MG Symptoms PRO 'Muscle Weakness Fatigability' score, Change from Baseline (Day 1) to Day 43 in MG Symptoms PRO 'Physical Fatigue' score, and Change from Baseline (Day 1) to Day 43 in MG Symptoms PRO 'Bulbar symptoms' score, will be analyzed in the same way as the main secondary endpoint based on the MG-ADL.

Time to MG-ADL response (≥ 2.0 -point improvement from Baseline [Day 1]) for each treatment cycle will be summarized using time-to-event methodology (Kaplan Meier).

The time between consecutive treatment cycles will be summarized in order to provide information on how long the effect of rozanolixizumab lasts, ie, how long it will take to introduce a new cycle.

The number and percentage of participants achieving Minimal Symptom Expression (MG-ADL score of 0 or 1) at any time during the Treatment and Observation Periods will be summarized by cycle and by dose administration in that cycle.

Additionally, the number of treatment cycles will be summarized by treatment group.

Further summaries will be described in the SAP.

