2.2.2.2 Other efficacy endpoints

For each 6-week treatment cycle and Observation Period (where applicable), improvement from Baseline (Day 1) to each scheduled assessment:

- MG-ADL responder (≥ 2.0 -point) within one treatment cycle
- QMG responder rate (≥ 3.0 -point) within one treatment cycle
- MG-C responder rate (≥ 3.0 -point) within one treatment cycle
- Time to MG-ADL response (≥ 2.0 -point) within one treatment cycle
- Minimal symptom expression (MG-ADL score of 0 or 1) at any time during Treatment and Observation Periods

For each 6-week treatment cycle and Observation Period (where applicable), change from Baseline (Day 1) to each scheduled assessment:

- In MG-ADL score within one treatment cycle
- In QMG score within one treatment cycle
- In MG-C score within one treatment cycle
- In MG Symptoms PRO 'Muscle Weakness Fatigability' score within one treatment cycle
- In MG Symptoms PRO 'Physical Fatigue' score within one treatment cycle
- In MG Symptoms PRO 'Bulbar symptoms' score within one treatment cycle

For each 6-week treatment cycle and Observation Period (where applicable), change from Baseline (Day 1) to Day 43^a:

- In 5-level European quality of life 5 dimensions (EQ-5D-5L) within one treatment cycle
- In Myasthenia Gravis-Quality of Life (MG-QOL15r) within one treatment cycle

Note:

^a Day 43 = Visit 8 for the initial fixed cycle and Visit 7 for the subsequent cycles.

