3.2.2 Study periods

The study cycle consists of the following:

- Treatment Period: 6 weeks
- Observation Period: 16 weeks
- Non-treatment period

The following definitions for starting and entering the study periods for each cycle will be applied:

- **Treatment Period** starts with the first day of IMP in each cycle in MG0007 and ends after Day 43 or PEOT assessments. All participants in the Safety Set will be considered to have started the Treatment Period. A participant is considered to have completed the Treatment Period of each cycle if assessments from Treatment Period Day 43 are completed.
- **Observation Period** starts with one day after the end of the Treatment Period of each cycle and ends after the final assessments at Day 155 visit. Participants with assessment on any Observation Period day are considered to have started the Observation Period.
- **Non-treatment period** starts with one day after the end of the Observation Period of each cycle and ends before the start of next cycle or the EOS assessment.

A study participant is considered to have completed the study if he/she has completed all phases of the study including the Observation Period and the EOS visit assessments. The end of the study is defined as the date of the last visit of the last participant in the study.

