9.5 MG-ADL responder rate (≥ 2.0 points improvement from Baseline)

Study participants will be classified as MG-ADL total score responders at a scheduled visit if there is an improvement (decrease of at least a 2-points) from Baseline in the MG-ADL total score.

The number and percentage of observed MG-ADL responders at each scheduled post-Baseline visit will be summarized by study cycle, actual dose level received within study cycle, and RLZ total using descriptive statistics.

Additional summary of observed MG-ADL responders by fixed dose and weight subgroups will also be conducted as specified in [Section 4.9.2](#).

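### Minimal Symptom Expression is counted without regard to cycle Baseline, so participants already at MG-ADL 0 or 1 before the mandatory first cycle can be scored as achieving it

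*SAP*

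**What the plan says.** SAP Section 9.12 defines the endpoint as an absolute state: "The Minimal Symptom Expression is defined as MG-ADL score of 0 or 1". The table then reports "The number and percentage of participants achieving Minimal Symptom Expression at any time during the Treatment and Observation Periods", by study cycle and dose. Protocol Section 9.4.1 has the same rule: "MG-ADL score of 0 or 1) at any time during the Treatment and Observation Periods will be summarized by cycle". Neither section mentions the Baseline score.

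The endpoint list in SAP Section 2.2.2.2 (and in Protocol Section 3) is different. There, Minimal Symptom Expression stands under a heading that speaks of "improvement from Baseline (Day 1) to each scheduled assessment".

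Three further provisions bear on the count:

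- **Window.** Under SAP Section 3.2.2 the Treatment Period "starts with the first day of IMP in each cycle in MG0007".
- **Timing of the score.** Protocol Section 8.1.4 says that on dosing days the "PROs will be completed prior to dosing".
- **Who enters cycle 1.** Protocol Section 9.2.1 states that "every study participant, except those coming from MG0004, will start with an initial fixed mandatory cycle". Protocol Section 5.1 sets no minimum MG-ADL.

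**The concern.** A rate of participants achieving a state is normally read as the share who reached it on treatment. Here the rule does not separate reaching the state from already being in it. Carry-over is plausible: MG0003 has a 6-week Treatment Period and an 8-week Observation Period, after which its participants enter cycle 1 of MG0007 whether or not their symptoms have returned. Some could start at 0 or 1.

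Later cycles, and the first MG0007 cycle of MG0004 entrants, start on worsening. The mix of starting scores therefore differs between cycle 1 and later cycles by design. MG0007 exists to describe repeated cycles, so a reader will naturally compare the cycle columns. A higher cycle 1 rate could then reflect starting scores and not what the cycle did.

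The responder table shows the opposite effect. SAP Section 9.5 classifies a participant as a responder "if there is an improvement (decrease of at least a 2-points) from Baseline in the MG-ADL total score". A participant who starts at 0 or 1 cannot fall by 2 points, so is always a non-responder there while being eligible for success in Section 9.12.

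**Working it through.** The plan states no rate, effect size or count for this endpoint, so there is no figure to reproduce. The check traces the definitions and then sizes the effect under stated assumptions.

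**Step 1: can a Baseline score be counted?** The Treatment Period starts on the first dosing day (SAP 3.2.2). Data are analyzed by scheduled visit (SAP 3.2.1), and Table 1-2 of the protocol places Visit 1 (Baseline, Day 1), with an MG-ADL, under the Treatment Period. That score is taken before dosing and is the cycle Baseline under SAP 3.3. Read literally, it lies inside the window. SAP 9.5 and 9.6 both restrict their counts to post-Baseline results; SAP 9.12 does not.

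**Step 2: does excluding Day 1 solve it?** No. A participant at 0 or 1 at Baseline who is still there at the next visit meets the rule with a post-dose score.

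**Step 3: can such participants enter cycle 1?** Yes. For MG0003 entrants, worsening is assessed before the first dose (Protocol 9.2.1; Table 1-2, footnote c), but it is not stated as a condition for dosing. SAP 6.1 plans a yes/no tabulation of worsening, so entry without it is foreseen.

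**Step 4: are they rarer in later cycles?** They should be. The protocol's example of worsening is a rise of 2.0 MG-ADL points or 3.0 QMG points. A 2-point MG-ADL rise gives a score of at least 0 + 2 = 2. The share need not be zero, because the thresholds are examples and a QMG rise may prompt the cycle.

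**Step 5: size.** Let b be the share at 0 or 1 at cycle Baseline and p the rate among the others.

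- Rate under SAP 9.12 if all Baseline 0–1 participants count: b + (1−b)p
- Rate among those with Baseline of 2 or more: p
- Excess: b + (1−b)p − p = b(1−p)

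Neither b nor p is in the documents. Both ranges below are assumptions. Each cell gives the rate shown, with the excess in percentage points in brackets.

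| b | p = 20% | p = 30% | p = 40% |
|---|---|---|---|
| 0% | 20.0% (0) | 30.0% (0) | 40.0% (0) |
| 2% | 21.6% (1.6) | 31.4% (1.4) | 41.2% (1.2) |
| 5% | 24.0% (4.0) | 33.5% (3.5) | 43.0% (3.0) |
| 10% | 28.0% (8.0) | 37.0% (7.0) | 46.0% (6.0) |
| 15% | 32.0% (12.0) | 40.5% (10.5) | 49.0% (9.0) |
| 20% | 36.0% (16.0) | 44.0% (14.0) | 52.0% (12.0) |

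At b = 10% and p = 30%, 10/37 = 27% of those counted as achieving the state were in it before dosing.

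If only post-dose scores were counted, and a share s of the Baseline 0–1 participants had at least one such score of 0 or 1, the excess would be bs + (1−b)p − p = b(s−p). So b(1−p) is exact on the literal reading and an upper limit otherwise.

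**The case against.** The strongest reply is that the Day 1 reading is an inference. SAP 9.12 never says that the Baseline score counts, and a Baseline score cannot be an improvement on itself, so the Section 2.2.2.2 heading points the other way. For direct MG0003 entrants, the MG0003 end-of-study assessments may serve as Baseline (Protocol 4.1.1). If dated before the first dose, they fall outside the Treatment Period by date, although they remain the Visit 1 record by visit. This stands. It does not dispose of the point, because staying at 0 or 1 is still counted and is not an improvement either.

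Second, the share at 0 or 1 is unknown and may be near zero. MG0003 enrolled people with moderate to severe symptoms. Gap-period entrants must be MGFA Class II to IVa (Protocol 10.12), and MG0004 entrants, who start on worsening, dilute the pooled cycle 1 share. This also stands, and is why the range begins at zero.

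Third, Baseline scores are reported anyway: MG-ADL and its category below 5 or 5 and above (SAP 6.2), and scores and changes by cycle with listings (SAP 9.1). These let a reader see that Baselines differ. However, the cut at 5 does not isolate scores of 0–1, and the Baseline-category subgroup in SAP 4.9.1 covers MG-ADL score and change, not this endpoint.

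A reader might also set this table and the SAP 9.5 table side by side as if they shared a denominator. The documents do not support that. SAP 3.1 bases efficacy percentages on participants with observed data for the variable concerned; SAP 9.5 is a rate per visit, and SAP 9.12 is a rate at any time in the cycle.

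**Conclusion.** The concern holds as a gap in the endpoint rule. As written, SAP 9.12 can credit a pre-dose state as achieved, chiefly in cycle 1 among MG0003 entrants, and it does not match the heading under which the endpoint is listed. The excess is b(1−p): 0 to 16 percentage points for assumed b of 0–20% and p of 20–40%, and nothing if no one starts at 0 or 1.

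Three stronger readings are tempting but unsupported. The documents do not state that Day 1 is counted. They do not show that any particular share of participants starts at 0 or 1, and a score of 1 is not freedom from symptoms. Nor do they show that the tabulated rate will fall across cycles; that follows only if b is appreciable in cycle 1 and the rate among the others does not rise enough to offset it.

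The consequence is limited to interpretation. Minimal Symptom Expression is one of the other efficacy endpoints, summarized without testing, so no error rate or sample size is affected. A correction is still worthwhile because the table is by cycle and the remedy is cheap.

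**What to change.** In SAP 9.12:

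- Count only MG-ADL totals of 0 or 1 recorded after the first dose of the cycle.
- Report the rate among participants whose cycle Baseline MG-ADL is 2 or more.
- Show the number already at 0 or 1 at cycle Baseline in a separate row. The all-participant rate may stay beside it.
- Say where a total between 1 and 2 belongs. SAP 13.3 imputes missing items to one decimal place, so such totals can occur: seven items summing to 1 average 0.14, imputed as 0.1, for a total of 1.1.

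Record the change in SAP 3.9, because restricting the denominator departs from Protocol 9.4.1. Optionally, add the SAP 9.5 responder rate in the same Baseline subset as a supplementary line.

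This costs a short text change, a changed denominator and an extra row, using data already collected. The downside is that the cycle 1 rate may look slightly less favourable.

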10 PHARMACOKINETICS AND PHARMACODYNAMICS

All PK and PD analyses tables and figures described in this section will be performed on the SS by study cycle and dose level received within the cycle and RLZ total as described in [Section 3.6](#). All listings will be presented using FAS.

10.1 Pharmacokinetics

Individual plasma concentrations of rozanolixizumab will be summarized by study cycle, actual dose level received within study cycle, RLZ total, actual dose (in mg) and scheduled sampling day using n, arithmetic mean, median, SD, minimum, maximum, geometric mean (geomean) with associated 95% CI, and geometric coefficient of variation (geoCV) (assuming log-normally distributed data).

The following rules will apply for PK data listings and summaries:

- Values below the LLOQ will be reported as BLQ.
- Descriptive statistics of concentrations will be calculated if at most 1/3 of the individual data points at a timepoint are missing or are not quantifiable (<LLOQ). Values that are BLQ will be replaced by the numerical value of the LLOQ/2 in this instance. If more than 1/3 of the individual data points at a timepoint are missing or are not quantifiable, then only n, minimum, median and maximum will be presented. The other descriptive statistics will be left blank.
- If n<3, then only the n, minimum and maximum will be presented. If no study participants have data at a given timepoint, then only n=0 will be presented.
- The 95% CI lower and 95% CI upper should be left blank if the SD (or equivalently, the geoCV) is 0.
- The geoCV will be calculated using the following formula where SD is the standard deviation from the log-transformed data

$$\text{geoCV}(\%) = \sqrt{\exp(\text{SD}^2) - 1} \times 100.$$

Individual concentrations of rozanolixizumab will be listed by treatment group for each cycle and will include the actual sampling time in days relative to the previous dose, the IgG observed at the same visit, the ADA titer observed for the binding assay and the NAb titer for the same visit, IgG and IgG subclasses, and MG-ADL change from baseline for the corresponding visit.

10.2 Pharmacodynamics

10.2.1 Total serum IgG and IgG subclasses

Total serum IgG concentrations and IgG subclasses will be summarized by study cycle, actual dose level received within study cycle, overall, and time point for observed values, change from Baseline, and percentage change from Baseline for each cycle. For the analysis of the IgG data, in case rescue therapies are taken, the data up to (not including) the start date of rescue therapy and the data 8 weeks after the start date of rescue therapy will be utilized for the summary tables, ie the data from (including) start date of rescue therapy, to 8 weeks after start date of rescue therapy will be excluded from summary analysis. In cases where a study participant drops out, no missing value imputation will be performed for the IgG.

The maximum change from Baseline in total serum IgG (absolute and percentage change) will be reported in the listing and summarized by study cycle, actual dose level received within study cycle, and RLZ total. If there is no decrease from Baseline in total serum IgG in a given study participant, the maximum change will be reported as the smallest increase from Baseline.

Additionally, summary of total IgG by fixed dose and weight subgroups will be conducted as specified in [Section 4.9.2](#).

Median and median percentage change from Baseline values in total serum IgG will be plotted over time by study cycle, actual dose level received within study cycle, and RLZ total with Baseline bodyweight groups (<50kg, 50kg-<70 kg, 70kg-<100kg, \geq 100kg) overlaid on the same plot.

Spaghetti plots will be provided for absolute IgG and percentage change from baseline in IgG over time stratified by treatment group and Baseline bodyweight group (<50kg, 50kg-<70 kg, 70kg-<100kg, \geq 100kg) where the Baseline bodyweight group is multipaneled or overlaying with different colors within each treatment group for each cycle.

A boxplot of maximum percentage from Baseline in total IgG up to Day 43 will be generated by study cycle and administered dose as specified in [Section 4.9.2](#).

A subject plot for MG-ADL, QMG, and IgG over time for participants with weight below 50kg will also be provided.

Serum concentrations of total IgG and IgG subclasses will be listed together with concentrations of rozanolixizumab, ADA and NAb sample status and titer, MG-specific autoantibodies, MG-ADL change from Baseline, as specified in [Section 10.3.2](#). The IgG values that were excluded from summary analysis will be flagged in listing. A separate listing of total IgG for participants who used manual push will also be provided.

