6.5.4 Rescue medication

The study site will supply rescue therapy that will be obtained locally. Rescue therapy will be given as per standard of care and at the discretion of the Investigator. Study participants who continue to experience moderate to severe symptoms despite treatment with rozanolixizumab may be treated with the following as rescue therapy:

- IVIg
- SC Ig
- PEX, or plasmapheresis
- iv corticosteroids at a higher dose than previous oral dose

Participants who are treated with rescue therapy during the Treatment Period are not eligible to receive any further treatment with rozanolixizumab. Study participants must complete the first 8 weeks of the Observation Period after the last dose of rozanolixizumab prior to completing the EOS visit assessments, and subsequently will be withdrawn from the study (Section 4.4).

Those patients who received rescue therapy during the observation or no treatment with rozanolixizumab periods may continue in the study at the Investigator's discretion and after discussion with Medical Monitor and/or UCB Study Physician. The following cycle of rozanolixizumab should in general not start earlier than 4 weeks following the last dose of IVIg, SC Ig, or iv corticosteroids or the last PEX session, unless there is a medical reason, and an earlier treatment initiation is being considered █ for the study participant as agreed upon with the Medical Monitor and/or UCB Study physician.

The date and time of rescue medication administration as well as the name and dosage regimen of the rescue medication must be recorded.

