9.4.2.2 Pharmacodynamic analyses

For all other endpoints relating to PD endpoints, descriptive statistics for the value, change from Baseline, and percentage change from Baseline will be tabulated by dose arm, and time point for the SS for each cycle. The PD endpoints will include serum total IgG, IgG subclass levels, and anti-MuSK and -AChR autoantibodies.

For the analysis of the IgG data, in case rescue therapies are taken, only the data up to the start date of rescue therapy will be utilized for the summary tables. Listings will contain all IgG data and the measurements of study participants, which have been excluded from the summary tables. In cases where a study participant drops out, no missing value imputation will be performed for the IgG. Absolute and relative IgG reduction for a cycle will be calculated with the cycle Baseline value as reference. As for safety, the IgG reduction analyses will be compared between cycles.

Population PD or population PK/PD analyses may be conducted for the PD variables of interest. Details of such PD or PK/PD analyses will be described in a separate DAP. The results of the analyses will not be reported in the CSR but in a separate report.

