3.9 Changes to protocol-defined analyses

In the protocol section 9.2.1, the intercurrent events to be considered are the use of rescue therapy prior to Day 43 and permanent treatment discontinuation (or withdrawal from study) due to TEAEs. In the SAP, we consider use of rescue therapy prior to Day 43 and permanent treatment discontinuation due to TEAEs as intercurrent events.

In the protocol, the treatment policy strategy is described for the analysis meaning that all data was planned to be analyzed regardless of study participants receiving treatment with rescue therapy. Summaries will also be presented for the efficacy endpoints where participants will be censored at the time that they take rescue medication. In the SAP, time to MG-ADL response will be analyzed censoring the data at the time of the use of rescue therapy and all other efficacy endpoints will be summarized following treatment policy.

Protocol amendment 3 did not mention how to treat IgG when participants receive rescue therapy. In the SAP, the IgG values up to and including 8 weeks after start date of rescue therapy will be excluded from the analysis.

In the protocol section 8.3.1, Hy's law is defined as $>3 \times \text{ULN}$ ALT or AST with coexisting $>2 \times \text{ULN}$ total bilirubin in the absence of $<2 \times \text{ULN}$ ALP, with no alternative explanation for the biochemical abnormality (ie, without waiting for any additional etiologic investigations to have been concluded). In this SAP, Hy's law is defined as (AST or ALT $\geq 3 \times \text{ULN}$) and TBL $\geq 2 \times \text{ULN}$ and ALP $< 2 \times \text{ULN}$ to be consistent with Rozanolixizumab program SAP.

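### The 8-week IgG exclusion runs from the first day of rescue, so a long rescue course leaves the next-cycle IgG baseline less protected than a single-day course does

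*SAP*

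**What the plan says.** SAP 10.2.1 (total serum IgG and subclasses) uses IgG up to the day before rescue and again from 8 weeks after rescue began: values from the start date, included, "to 8 weeks after start date of rescue therapy will be excluded from summary analysis". SAP 3.9 gives the same rule: "the IgG values up to and including 8 weeks after start date of rescue therapy will be excluded from the analysis". Neither section mentions a last dose, a stop date, ongoing rescue or a repeat course.

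The protocol treats rescue as something that can extend over time. Section 6.5.4 sets no maximum length: "Rescue therapy will be given as per standard of care and at the discretion of the Investigator". Its own waiting time before another cycle is counted from the end of rescue: the next cycle "should in general not start earlier than 4 weeks following the last dose of IVIg", SCIg or iv corticosteroid, or the last PEX session, with exceptions by agreement.

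The protocol also has its own IgG rule. Section 9.4.2.2 says that after rescue "only the data up to the start date of rescue therapy will be utilized for the summary tables". SAP 3.9 nevertheless introduces the new rule by stating "Protocol amendment 3 did not mention how to treat IgG when participants receive rescue therapy".

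**The concern.** The exclusion exists because immunoglobulin infusion adds IgG and plasma exchange removes it, so values soon after either are not a clean reading of rozanolixizumab's effect. That influence runs from the last administration, but the SAP's window runs from the first. The longer the rescue course, the less of the 8 weeks is left once it ends, so heavier rescue receives less protection.

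What is at stake is the pharmacodynamic description. Under SAP 3.3 the last value on or before the first infusion of a cycle is that cycle's baseline. An affected baseline feeds the change, percentage change and maximum change in IgG for the cycle. Those feed the dose-by-weight summaries and the boxplot up to Day 43 (SAP 4.9.2 and 10.2.1), and the table of IgG change by ADA category (SAP 10.3.2). The listing flags only excluded values, so a re-admitted value would carry no mark.

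**Working it through.** There is no planned figure to reproduce; the check is date arithmetic.

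**Inputs**
- Exclusion window: rescue start to start + 56 days, inclusive (SAP 10.2.1, 3.9).
- Usual earliest restart: 28 days after the last rescue dose or session (Protocol 6.5.4).
- IgG samples in subsequent cycles: Days 1, 22, 43, 99 and EOS (Protocol Table 1-3). After Day 43 of the initial cycle: Day 71 and EOS (Table 1-2).
- D, days from first to last rescue dose: not in the documents. Assumed range 0 to 84.

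**Formulas**
- Protection after the last rescue dose = 56 − D.
- Days from rescue start, at the earliest usual restart: next-cycle Day 1 = D + 28; Day 22 = D + 28 + 21 = D + 49; Day 43 = D + 28 + 42 = D + 70.
- A value is admitted if its day exceeds 56.

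| D | 56 − D | Day 1 | Day 22 | Day 43 |
|---|---|---|---|---|
| 0 | 56 | 28, out | 49, out | 70, in |
| 4 | 52 | 32, out | 53, out | 74, in |
| 14 | 42 | 42, out | 63, in | 84, in |
| 28 | 28 | 56, out | 77, in | 98, in |
| 29 | 27 | 57, in | 78, in | 99, in |
| 42 | 14 | 70, in | 91, in | 112, in |
| 56 | 0 | 84, in | 105, in | 126, in |
| 84 | −28 | 112, in | 133, in | 154, in |

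Day 22 is admitted when D > 7 and Day 1 when D > 28. Day 43 is admitted under either anchor. In every row Day 1 lies exactly 28 days after the last rescue dose, yet it is excluded for D up to 28 and admitted beyond that. If restart is r days after the last dose instead of 28, Day 1 is admitted when D + r > 56, so an agreed early restart brings the baseline closer still to rescue.

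**Effect of the baseline.** If the Day 1 value is B + δ instead of B, the absolute change Y − B becomes Y − B − δ at every visit of the cycle, and the percentage change 100(Y/B − 1) becomes 100(Y/(B + δ) − 1). The documents give no size for δ.

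**Where values cannot leak, or hardly can**
- *Treatment Period rescue.* No more drug is given: "Participants who are treated with rescue therapy during the Treatment Period are not eligible to receive any further treatment with rozanolixizumab". With EOS 56 days after the last rozanolixizumab dose and rescue starting on or after that dose, EOS falls inside the window. With the +2-day visit allowance it falls outside only if rescue began on the day of that dose or the day after.
- *Observation Period rescue, from Day 44.* The window ends no earlier than Day 44 + 56 = Day 100. The initial-cycle Day 71 sample (at latest Day 78) is always excluded. The subsequent-cycle Day 99 sample (at latest Day 106) escapes only if rescue starts on Days 44 to 49 and the visit is late.
- *On-rescue values.* These need D > 56 and a sample in that time. The no-treatment visits schedule no IgG sample, so this is mainly EOS.

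**With the window counted from the last dose.** Protection is 56 days for any D. At the earliest usual restart, Day 1 (28 days after) and Day 22 (49 days after) are always out, and Day 43 (70 days after) is in.

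**The case against.** The strongest reply is that the protocol already protects the next cycle. With the usual restart, no next-cycle sample lies closer than 4 weeks to the last rescue dose, however long the course. Protocol Table 10-2 uses the same 4 weeks as the treatment-free period for immunoglobulin and PEX before Baseline in gap-period participants. This stands. A reader might infer from 56 − D that washout in the next cycle falls to zero, or that values taken during rescue routinely enter the summaries. The documents do not support that: the restart rule normally holds a 28-day floor, and on-rescue values need a course of more than 56 days with an EOS or unusually timed sample.

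It does not remove the point. The SAP chose 8 weeks, and under that choice a value 28 days after a single-day course is too close to use. The same distance cannot become acceptable because the course was longer.

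Other parts of the reply also have force. No document gives a course length or a count, so prolonged SCIg is an assumption. Iv corticosteroids are rescue too, but the documents describe no comparable direct effect on IgG. If each infusion or session is recorded with its own start date and each reopens the window, the gap closes. The SAP does not say so, and one sentence would settle it. Finally, the analyses are descriptive, PD falls under the other objectives, and restoring the protocol's cut at rescue start would make the question disappear.

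**Conclusion.** The concern holds in a limited form. The anchor is explicit in both SAP sections and nothing else in the documents resets it. The practical consequence is confined to immunoglobulin or PEX rescue in the observation or no-treatment periods: at the usual restart, the next-cycle baseline is admitted when D > 28 days and Day 22 when D > 7 days, where a single-day course would have both excluded.

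This assumes that rescue is dated by the start of the course and that restart is 28 days after its end. The number of participants affected cannot be derived from the documents. No test or efficacy endpoint depends on it, so this is a low-priority improvement.

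One related error is certain: SAP 3.9 is wrong that the protocol does not address IgG after rescue. A reader might infer that re-admission itself is therefore invalid. The documents do not show that; they show a departure from Protocol 9.4.2.2 that has not been recorded as one.

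**What to change.** 1. In SAP 10.2.1 and 3.9, exclude total IgG and subclass values from the start of rescue to 8 weeks after the last recorded dose or PEX session, and throughout ongoing rescue. State that each recorded administration or session reopens the window.
2. When a stop date is missing, use the last recorded administration or session date. Protocol 6.5.4 requires administration dates to be recorded. PEX is identified from the procedure page, and the documents describe no stop date for it (SAP 6.4). Do not borrow the SAP 4.2.2 default: it turns an unknown stop date into the discharge or data cut-off date, which here could remove all of a participant's later IgG.
3. State that a cycle baseline inside the window is treated as missing, and how the SAP 3.3 fallback to an earlier value then applies. This gap already exists for courses of up to 28 days.
4. Correct SAP 3.9: cite the rule in Protocol 9.4.2.2 and list the re-admission of later IgG as a deliberate change.

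The cost is a few sentences and a revised derivation. A few more IgG values leave the summaries, but they stay flagged in the listing.
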